Twenty subjects will be performing low-resistance exercise with (BFRT). Intervention will start at least seven days after initial evaluation, so it does not influence measures of real-time physical activity. We will use a log to register exercise completion and to record bilateral knee pain before, during and after each intervention session at the PT-Lab. BFRT will be done using low-resistance (20-30% of 1-repetition maximum) leg extensions, leg curls, and sit-to-stand exercises. Performing exercises at this intensity with the blood flow restricted by a cuff, which maintains arterial inflow while obstructing venous outflow distal to the occlusion site, creating a metabolic environment that alters neuromuscular activity and improve quadriceps muscle volume and strength comparable to traditional high-resistance training ($\geq 70\%$ of 1-repetition maximum) in older adults. BFRT cuff will be placed around subject's thighs prior to exercise. Cuff pressure to be used for the BFRT will be established by placing the cuff on the proximal end of the thigh and inflated until full occlusion is achieved. A portable Doppler will be used to capture auscultatory signal of the posterior tibial artery for this assessment. Based on the pressure (mmHg) used to achieve full occlusion, the BFRT cuff ((B)StrongTM; Park City, UT) will be set up at 50% of that pressure to start the intervention and will progress up to 80% pressure according to subject's tolerance. This adjustment will be done once a week in a PT lab, when subjects will have the BFRT cuff pressure increased by 5-10% and will perform the intervention supervised by a trained researcher. Intervention will consist of 10-minute warm-up on a stationary bike, 4 sets (30, 15, 15, and 15 repetitions) of each proposed exercise bilaterally, and stretching exercises of the lower extremity as cool-down. Subjects will perform a 10-repetition submaximal testing for 1-repetition maximum to estimate the resistance to be used for each exercise. We will use adjustable ankle weights (1-20 pounds) for leg extensions and leg curls, and a weighted vest (3-120 pounds) for sit-to-stand exercise. Total time to complete intervention is ~40 minutes. Subjects will wear BFRT cuffs only during the low-resistance exercise (~15-20 minutes). The maximum time recommended to wear the BFRT cuffs is 20 minutes.

Study visit procedures:

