- Physical Functional Assessment to include self-selected gait speed, timed 5 chair rise, single leg stance time, timed-up and go test, stair ascend/descend test, and 6-minute walk test
- Patient-Reported Outcomes Measurement (PROMIS)
- RAND-36-item Health Quality of Life Survey
- Subjects will be provided with an actigraph monitor device and asked to wear it for one-week to assess a baseline physical activity prior to BFRT sessions

Visit 02 – Visit 07 (Treatment Weeks 1 through Week 6; all procedures completed for research)

One week after baseline visit, subjects will complete 12-18 sessions of low-intensity blood flow restriction training (BFRT), two to three times a week, for six weeks, based on patient willingness/availability. A minimum of 12 sessions is required for study participation. BFRT sessions will be completed as described above at the UT Physical Therapy Research Lab. An exercise and pain log will be completed during and after each intervention session. All training sessions will be provided by qualified providers who are also IRB approved research team members.

Visit 08 (Pre-operative Follow up Week 7; all procedures completed for research)

A pre-operative follow-up visit will be scheduled one week after completion of BFRT intervention sessions. Subjects will be asked to complete the following:

Vital signs

Blood sample will be collected (approx. 30ml) to assess inflammatory biomarkers (research).

Whole-body DEXA scan (research)

Physical Functional Assessment to include self-selected gait speed, timed 5 chair rise, single leg stance time, timed-up and go test, stair ascend/descend test, and 6-minute walk test

Patient-Reported Outcomes Measurement (PROMIS)

RAND-36-item Health Quality of Life Survey

Actigraph monitor provided at the end of Treatment week 6 and collected at time of pre-op follow up Week 7

Visit 09 - Routine Total Knee Replacement Surgery (Routine Standard of Care)

Routine knee surgery will be performed per standard of care. Results will be requested for research purposes

Visit 10 (Post-operative Follow up 8-weeks after TKR surgery; all procedures completed for research)

Same procedures as V08 will be completed

Visit 11 – this is a virtual research visit only. Subjects will be asked to mail actigraph monitoring device by mail in a prepaid envelope provided by the study team. This will qualify as the end of study visit.

Adverse events will be monitored at each visit.

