biomarkers. The laboratory will use the 'MILLIPLEX® MAP Human High Sensitivity T Cell Magnetic Bead Panel' to assess a panel of 8 inflammatory biomarkers: Interleukin (IL)-1 β , IL-2, IL-5, IL-6, IL-10, IL-12p70, IL-13 and Interferon- γ .^{32,53}

Additional Measures

1) Demographic factors: age, gender, ethnicity, marital and educational status

2) Biomedical factors

a) Medication prescribed and over-the-counter used for pain will be recorded in the medication form. We will record the current and highest dosage of any pain medication used during the last month (when performing pre-intervention evaluation), or during the interval between evaluations.

b) Comorbidity data will be collected using the Cumulative Illness Rating Scale.⁵⁴

c) Body Mass Index will be calculated as the subject's body weight divided by the height squared.

d) Knee Range of Motion will be measured in the supine position utilizing a standard goniometer. The available range of knee flexion and extension will be measured. When measuring passive knee extension, the heel will be elevated on a bolster to ensure the end range of extension is achieved.

e) Knee Pain in both knees (surgical and non-surgical sides) will be measured using an 11-point (0 to 10) numeric scale. The scale will be anchored at one end with the phrase "no pain" (0) and at the other end with the phrase "worst imaginable pain". Subject will be instructed to report the greatest pain during last 24h.^{55,56}

Research personnel will keep track of assessment procedures using a checklist. An exercise log will be used to track delivered exercise sessions. All questionnaires will be self-administered using Redcap.

Although subjects are asked to not participate in any exercise-related program during the study period, research personnel will track exercises performed by subjects on a log.

Study personnel reserve the rights to discontinue delivery of intervention if subject presents with muscle or joint pain that cannot be resolved by administering over-the-counter pain medication.

Research personnel will ensure to follow-up with subjects who have discontinued the study in regards to their recovery from muscle or joint flare-ups due to study intervention to monitor AE, SAE and/or UPIRSOs.

Statistical Considerations

Statistical Hypotheses

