State the formal and testable null and alternative hypotheses for primary and key secondary endpoints, specifying the type of comparison (e.g., superiority, equivalence or non-inferiority, dose response) and time period for which each endpoint will be analyzed.

Our hypotheses are that:

- our exercise protocol will be safe, compliance with intervention will be >80% of completed exercise sessions, and retention will be >80% of subjects.

- Subjects will demonstrate improvement in muscle strength and morphology, physical function, quality of life, physical activity, and biomarkers of inflammation from T0-T1 (before TKR), which will hold true from T0-T2 (after TKR).

Sample Size Determination

Include number of participants to recruit, screen, and enroll to have adequate power to test the key hypotheses for the study. Provide all information needed to validate your calculations and judge the feasibility of enrolling and following the necessary number of participants.

Due to the exploratory (pilot) nature of the study, we aim to recruit 20 subjects to answer our question on the feasibility of our exercise protocol.

Populations for Analyses

Clearly identify and describe the analysis datasets (e.g., which participants will be included in each).

This is a single group pre-post design. All participants recruited will be assessed regarding compliance, adherence, and safety of our exercise protocol. Data on demographics, biomedical factors, and outcomes measures (i.e., muscle

strength and morphology, physical function, quality of life, physical activity, and biomarkers of inflammation) will be entered in the dataset for each timepoint.

Statistical Analyses

Include analysis of primary efficacy endpoints, secondary endpoints, safety analyses, and any planned interim analyses. Descriptive statistics on adverse events (i.e., joint and/or muscle pain) during exercise sessions and at each timepoint will be provided. Data on secondary outcomes (i.e., muscle strength and morphology, physical function, quality of life, physical activity, and biomarkers of inflammation) will be compared between T0-T1, T0-T2 and T1-T2.

Due to the small sample size (N=20) we will conduct a non-parametric paired difference test (i.e., Wilcoxon signed-rank test) to identify whether those comparisons are statically significant.

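### The protocol does not separate stopping BFRT from leaving the study, so the T1 and T2 comparisons may rest on those who tolerated it, and retention is ambiguous

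*Combined protocol and SAP*

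**What the plan says.** Two adjacent sentences in Item 6, Additional Measures, deal with stopping. The first concerns treatment, where over-the-counter medication has not settled the pain: "Study personnel reserve the rights to discontinue delivery of intervention if subject presents with muscle or joint pain that cannot be resolved". The second concerns the study: "Research personnel will ensure to follow-up with subjects who have discontinued the study in regards to their recovery from muscle or joint flare-ups". The rest of that second sentence ties the flare-ups to the training and gives the purpose of the contact: "due to study intervention to monitor AE, SAE and/or UPIRSOs".

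Under Study visit procedures, the entry for Visits 02 to 07 plans 12 to 18 sessions over six weeks and adds: "A minimum of 12 sessions is required for study participation". Visit 08 (T1, labelled Week 7) is set one week after the training sessions have been completed. Visit 10 (T2) falls eight weeks after surgery. The schedule ends with: "Adverse events will be monitored at each visit".

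Populations for Analyses states: "All participants recruited will be assessed regarding compliance, adherence, and safety of our exercise protocol". It names no population for the strength, function, activity or biomarker comparisons. Statistical Analyses compares these outcomes between time points with a Wilcoxon signed-rank test and gives no method for missing pairs. On safety it says: "Descriptive statistics on adverse events (i.e., joint and/or muscle pain) during exercise sessions and at each timepoint will be provided".

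Statistical Hypotheses sets targets of more than 80% for session compliance and for subject retention. The Data Analysis Plan measures retention by counting dropouts, without defining a dropout, and intends the change values to inform the sample size of a larger trial. That section numbers the time points T1 to T3; here T0, T1 and T2 are used as in Item 4.

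**The concern.** Item 3 gives the open question as whether patients awaiting knee replacement can tolerate BFRT. Subjects stopped for pain are the most direct evidence on it. If stopping treatment also ends assessment, three things follow.

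- Their T1 and T2 values are missing for a reason related to how they responded, and a paired test leaves them out.
- The change values carried into the next trial's sample size describe only those who could do the training.
- Retention, part of the primary feasibility outcome, mixes intolerance of the intervention with unwillingness to be assessed. For a feasibility study these are different findings that call for different responses.

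**Working it through.** **1. The passages side by side.** Take a subject whose BFRT is stopped for pain after session 6 (a hypothetical case).

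- *Status.* Additional Measures allows the stop. The next sentence calls those followed for intervention-related flare-ups subjects who have discontinued the study. The session minimum, read literally, is no longer met. No sentence says that the subject remains enrolled.
- *T1 date.* Visit 08 is timed from completion of the sessions, which this subject never reaches, so no date is defined.
- *T2.* Visit 10 is timed from surgery, so a date exists, but nothing says that the subject is invited.
- *Analysis.* All recruited participants are assigned to compliance, adherence and safety only. Without a T1 or T2 value there is no paired difference.
- *Retention.* Whether the subject is a dropout is not stated.

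**2. Retention.** Inputs: N = 20 (Sample Size Determination) and a target of more than 80% (Statistical Hypotheses).

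- 16/20 = 80% does not exceed 80%; 17/20 = 85% does. At least 17 must be retained.
- Four pain stops and no other loss: 16/20 = 80% (missed) if they count as dropouts; 20/20 = 100% (met) if they stay and attend.
- Three pain stops and no other loss: 17/20 = 85% or 20/20, met either way.
- Three pain stops and one true withdrawal: 16/20 = 80% (missed) or 19/20 = 95% (met).

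**3. Size of a completer-only bias.** The documents give no expected number of stops and no expected change, so both are assumptions here. Let d of 20 subjects stop and have no later data, let completers change by M on average, and let stoppers change by cM.

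All-enrolled mean = [(20 − d)M + d·cM] / 20.

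With c = 0, the completer mean divided by the all-enrolled mean is 20/(20 − d):

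| d | ratio | overstatement |
|---|---|---|
| 1 | 20/19 | 5% |
| 2 | 20/18 | 11% |
| 3 | 20/17 | 18% |
| 4 | 20/16 | 25% |
| 6 | 20/14 | 43% |

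With c = −1 (stoppers worsen by as much as completers gain), the all-enrolled mean is (20 − 2d)/20 of the completer mean: 0.70 for d = 3 and 0.60 for d = 4. With c = 1 there is no bias. These figures concern mean change, which bears on the descriptive change values; they do not describe the behaviour of the Wilcoxon test.

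**4. Adverse events.** Step-by-Step Methods has staff "record bilateral knee pain before, during and after each intervention session at the PT-Lab", so pain that leads to a stop is logged. Events are monitored at visits, which include the training weeks. After discontinuation, the described contact concerns muscle or joint flare-ups from the intervention. An event of another kind, in a subject with no further visits, has no described route into the data.

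**The case against.** A reader might infer that adverse events will come only from those who tolerated BFRT. The documents do not support that. The sentence on follow-up gives adverse event, SAE and UPIRSO monitoring as its purpose, pain is recorded at every session, and safety is assessed in everyone recruited. Only the narrower gap in step 4 remains.

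A reader might also infer a rule that a pain stop ends study participation. The documents contain no such rule. The two sentences can be read as covering different people, and nothing bars a stopper from Visit 08 or 10. The session minimum follows the two-to-three-times-weekly schedule, and 2 × 6 = 12, so it may be only the least a subject must agree to. This is fair: the literal reading is natural but inferred. It does not remove the point, because the text is also silent on keeping such subjects in, and T1 has no date for them.

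Nor is it right that intolerance and refusal could never be told apart. The exercise and pain logs, the flow chart and the planned time-to-dropout analysis hold part of the information. What is missing is the definition that turns those records into a retention figure.

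Finally, the bias figures are wholly assumed. That stands, and they are offered only as a range.

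**Conclusion.** The point holds as a gap in definition with practical consequences. The protocol does not distinguish stopping the intervention from leaving the study, and does not say whether those who stop are assessed at T1 and T2. Followed literally, the T0–T1 and T0–T2 comparisons would be completer-only.

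A bias towards benefit is probable, on the assumption that subjects stopped for pain change less favourably than the rest. Its size is unknown: under no change in stoppers it is 18% with three of 20 stopped and 25% with four. The effect on retention needs no assumption about change. With four pain stops and no other losses, the same events give a missed target or full retention. The safety gap is limited to events other than flare-ups after a subject stops attending. The plan should be amended, but the point does not invalidate the design.

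**What to change.** Leave the pain-stopping rule as it is and make these changes.

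1. In Item 6 (the Visit 02 to 07 entry and Additional Measures), define *discontinued intervention* separately from *withdrew from study*. State that a subject who stops BFRT, or completes fewer than 12 sessions, remains in the study.
2. Invite these subjects to Visits 08 and 10 on the original calendar, with T1 about seven weeks after the start of training and before surgery. Collect all adverse events, not only flare-ups, to Visit 10.
3. In Populations for Analyses and Statistical Analyses, include all enrolled subjects with available data in the T0–T1 and T0–T2 comparisons, and report the number of missing pairs with reasons.
4. In the Data Analysis Plan, report intervention discontinuation, with number and reasons, as a feasibility result separate from study retention.

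The cost is a short amendment and a few assessment visits, already planned for all 20 subjects, carried out in those who stop. The estimated change is likely to be slightly less favourable. Some pairs will still be missing, which is why item 3 asks for them to be reported.

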COVER PAGE

Official Study Title: Feasibility of Blood-flow Restriction Training Prehabilitation in Older Adults Awaiting Total Knee Replacement

NCT number: NCT06111690

IRB Approval Date: 09-05-2024

Unique Protocol ID: HSC20210590H

Protocol Template Form

Item 1 UTHSCSA Tracking Number	HSC20210590H
---	--------------

Item 2 Abstract / Project Summary	Provide a succinct and accurate description of the proposed research. State the purpose/aims. Describe concisely the research design and methods for achieving the stated goals. This section should be understandable to all members of the IRB, scientific and non-scientific. DO NOT EXCEED THE SPACE PROVIDED.
--	--

Purpose/Objectives: The overall aim of this research is to demonstrate that preoperative exercises (prehabilitation) using blood-flow restriction training (BFRT) is safe, well tolerated, improves muscle function, decreases functional limitation, and increases physical activity in older adults awaiting total knee replacement (TKR).

Research Design/Plan: This is a single group pre-post design study. Outcomes will be measured at baseline, after 6 weeks of prehabilitation, and 8 weeks after TKR.

Methods: Twenty individuals ≥ 60 years old awaiting TKR due to diagnosis of end-stage knee osteoarthritis who meet the inclusion/exclusion criteria will be invited to participate in a 6 weeks of low-intensity BFRT prehabilitation. We will assess muscle morphology (i.e., cross-sectional area and intramuscular fatty content) using dual x-ray absorptiometry (DEXA) scan, quadriceps muscle strength using an isokinetic dynamometer, a battery of performance-based physical function, self-reported physical function and quality of life, and biomarkers of inflammation using blood serum. Feasibility assessment will be done by looking at safety (i.e., adverse events), compliance, and attrition rate.

Clinical Relevance: The low intensity prehabilitation program using BFRT may lead to improvements in muscle morphology and strength, as well as physical function before TKR. Since muscle weakness and functional limitations experienced preoperatively affect the recovery after TKR, these individuals may experience a significant benefit from our program. Thus, our program may allow patients undergoing TKR to perform daily activities early on postoperatively. Moreover, by increasing physical activity and preventing exacerbation of joint inflammation, our program might impact the general health in older adults after TKR.

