
Item 4
 
Purpose and rationale
 
Insert purpose, objectives and research questions/hypotheses here.
 
If you cut and paste from another document, make sure the excerpted material answers the question
	
Primary outcome: feasibility of BFRT during prehabilitation in older adults awaiting TKR.
 
Secondary outcomes: muscle strength and morphology (i.e., volume and quality), physical function, real-time physical activity and concentration of inflammatory biomarkers.
 
Endpoint: Baseline (T0), after 6 weeks of prehabilitation (T1) and 8 weeks postoperative (T2)
 
Justification for Endpoint: - T0 will provide overall idea on subjects' baseline characteristics of outcome-related data.
 
- T1 will provide data on safety, compliance and attrition rate of the BFRT prehabilitation program, as well as its effect on muscle strength and morphology, physical function, real-time physical activity and concentration of inflammatory biomarkers.
 
- T2 will provide data on the continuing effect of BFRT prehabilitation on muscle strength and morphology, physical function, real-time physical activity and concentration of inflammatory biomarkers postoperatively.
 
Rationale: The low intensity prehabilitation program using BFRT may lead to improvements in muscle morphology and strength, as well as physical function before TKR. Since muscle weakness and functional limitations experienced preoperatively affect the recovery after TKR, this population may experience a significant benefit from our program. Thus, the results of our investigations may allow patients undergoing TKR to perform daily activities early on postoperatively. Moreover, by increasing physical activity and preventing exacerbation of joint inflammation, our program might impact the general health in individuals after TKR.

Item 5 Study Population(s) Being Recruited
 
In your recruitment plan, how many different populations of prospective subjects do you plan to target? Provide number: 1
	
Identify the criteria for inclusion:
	
---	--	--

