Primary Outcomes: 1) Quadriceps muscle function:

1a. Strength will be measured using an isokinetic dynamometer (Biodex System 4 Pro, Shirley, NY). We will record the quadriceps femoris maximum voluntary isometric contraction (MVIC) as torque output (Nm). Subjects will be seated in the dynamometer's chair with their knee at 60 degrees of flexion. Subject position, stabilization, and gravity correction will be performed according with the Biodex manufacturer's guidelines. Subjects will exert as much isometric force as possible while trying to extend the knee against the force arm of the dynamometer. The MVIC will be the highest torque (Nm) of four trials.³³ Torque will be the variable used in data analysis. Strong verbal encouragement from the tester and visual feedback from the dynamometer screen will be provided during trials. Previous studies using this method in individuals with arthritis indicate that it was tolerated well and did not result in adverse effects.^{34,35}

1b. Cross-sectional area and Quality will be measured using a whole-body DEXA scan to investigate muscle composition of the thigh region bilaterally.^{36,37} Serial axial plane DEXA scan will be used to quantify changes in thigh muscles cross sectional area (CSA) and quality (i.e., amount of intramuscular fat) bilaterally. Subjects will be imaged in supine with the legs extended flat on the table. The scanner measures the absorption of two different energy levels of X-rays as they pass through the body. This information is used to create an image of the body that shows the distribution of bone, fat, and muscle tissue that have different X-ray attenuation. Using these differences in X-ray attenuation, the DEXA software is able to distinguish and quantify the amount of muscle and fat in a specific region of interest, such as the thigh muscles.

Secondary Outcomes:

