Data Analysis Plan: A flow chart will be prepared to identify and summarize issues in recruitment and retention, record total numbers screened, numbers excluded with reasons for non-participation, timing and frequency of dropout, etc. Retention will be assessed by frequency count of dropouts. Survival analysis of time to dropout may point to parts of the protocol that are difficult (e.g., very early dropout, loss to follow-up).

We will perform a descriptive summarization of demographic and baseline (T1) values of biomedical factors, and outcomes measures (i.e., muscle strength, physical function, quality of life, physical activity, and biomarkers of inflammation), post 6-week prehabilitation values (T2), and 12 weeks (T3) after TKR values. Then, change values from T1 to T2, and change values from T1 to T3 will be described stratified by intervention group. This information will be important to perform formal sample size and power computations for a future larger trial. Due to the small sample size, more attention will be paid to a trend towards a relatively smaller p-value rather than statistical significance based on a strict criterion (e.g., $\alpha=0.05$).

Item 7 Risks Section:

Complete the following table to describe the risks of all **research procedures** listed in Step 2, Institutional Form (items 28-34). *Do not list risks of Routine care procedures here.*

☒ N/A, Risks are described in the informed consent document – do not complete this table.

Research procedures	Risks
example: 
 History and physical Questionnaire Laboratory tests 
Add or delete rows as needed
	
List the reasonably expected risks under the following categories as appropriate:

	○

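### The plan aims to demonstrate safety and retention above 80%, but counts from 20 participants with no intervals can only estimate them, and imprecisely.

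*Combined protocol and SAP*

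**What the plan says.** Item 2 (Purpose/Objectives) gives the overall aim as demonstrating that the programme "is safe, well tolerated, improves muscle function", among other benefits. Item 4 names the primary outcome: "Primary outcome: feasibility of BFRT during prehabilitation in older adults awaiting TKR". It assigns safety, compliance and attrition data to T1, the assessment after six weeks of prehabilitation. Item 6 also carries the label "Primary Outcomes: 1) Quadriceps muscle function". The two labels need to be reconciled; this point follows Item 4.

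Under Statistical Hypotheses (Item 6) the plan hypothesises that "our exercise protocol will be safe, compliance with intervention will be >80% of completed exercise sessions", and that "retention will be >80% of subjects". The template prompt above those lines asks for testable hypotheses and a time period for each endpoint. The retention line gives no time period. Sample Size Determination cites the pilot nature of the study and says "we aim to recruit 20 subjects to answer our question on the feasibility of our exercise protocol".

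On analysis, the Data Analysis Plan says "Retention will be assessed by frequency count of dropouts". It adds a participant flow chart, including when and how often dropout occurs, and a possible survival analysis of time to dropout. Adverse events are to be summarised descriptively, per session and per time point, with a parenthesis that equates them with joint or muscle pain. Populations for Analyses states that "All participants recruited will be assessed regarding compliance, adherence, and safety of our exercise protocol"; retention is not named there.

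**The concern.** The analysis is descriptive, but the aim and hypotheses are worded as properties to be shown. Nothing in the plan connects the two. No interval goes with the retention count or the adverse-event summary, and no event type, rate or margin defines safe, so no result could contradict that hypothesis.

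At stake is what may be concluded on the Item 4 primary outcome. A bare 85% retention, or a bare absence of serious events, would sit beside hypotheses that it appears to confirm. The reader would not see how wide a range of true values fits the same data.

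Compliance has a further gap. The visit schedule in Item 6 allows 12 to 18 sessions, so a threshold of more than 80% of sessions has no fixed denominator.

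**Working it through.** **Inputs.** n = 20 (Sample Size Determination). Retention threshold above 80% (Statistical Hypotheses). Sessions 12 to 18 (Visit 02 to Visit 07). The plan gives no formula, power, precision target or expected retention for n = 20, so there is no figure of its own to reproduce. Three things are assumed: all 20 are in the denominator, the inequality is strict, and the true rates used below are illustrative.

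**Threshold as a count.** 0.80 × 20 = 16, and 16/20 is exactly 80%. More than 80% therefore means at least 17 retained.

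**Precision of retention.** Exact (Clopper-Pearson) 95% limits for x of n: lower = the 0.025 quantile of Beta(x, n − x + 1); upper = the 0.975 quantile of Beta(x + 1, n − x). At x = n the lower limit is 0.025^(1/20) = 0.832.

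| Retained | Observed | Exact 95% CI |
|---|---|---|
| 17/20 | 85% | 62.1% to 96.8% |
| 18/20 | 90% | 68.3% to 98.8% |
| 19/20 | 95% | 75.1% to 99.9% |
| 20/20 | 100% | 83.2% to 100% |

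Only 20/20 excludes 80%. A one-sided 95% limit does not change this: for 19/20 it is 78.4%. The chance of 20/20 is p^20, which is 0.90^20 = 0.12 or 0.95^20 = 0.36.

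**How often the threshold is met when retention is poorer.** P(X ≥ 17) = Σ C(20, k) p^k (1 − p)^(20 − k), for k = 17 to 20:

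- p = 0.70: 0.107
- p = 0.75: 0.225
- p = 0.90: 0.867

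The 0.225 does depend on sample size. Under the same rule with 100 participants (at least 81 retained) it would be about 0.10.

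**What demonstration would take.** An exact one-sided 5% test against 80% with at least 80% power needs 82 participants if true retention is 90%, or 30 if it is 95%.

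**Safety.** With 0 events in 20, the upper limit is 1 − 0.025^(1/20) = 16.8% (two-sided 95%) or 1 − 0.05^(1/20) = 13.9% (one-sided 95%). If the true rate were 10%, no event would be seen with probability 0.90^20 = 0.12.

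**Compliance denominator.** Twelve sessions are 12/12 = 100% of the smallest schedule but 12/18 = 67% of the largest. Exceeding 80% takes 10 sessions out of 12 (0.80 × 12 = 9.6) or 15 out of 18 (0.80 × 18 = 14.4). Ten would also fall short of the 12-session minimum that the visit schedule states.

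**The case against.** The strongest reply is that this is a single-group pilot, described as exploratory, which sets no error rate or decision rule for feasibility and disclaims strict significance criteria. On that view the thresholds are expectations and nothing is being tested. The plan also does more than count dropouts: it has the flow chart and the possible time-to-dropout analysis. Item 4 places attrition at T1. All recruited participants are already assessed for compliance and safety. Adverse events are monitored at each visit, and participants who discontinue are followed for adverse and serious adverse events. All of this stands. It narrows the gap to four things: intervals, a criterion or estimate behind the word safe, a time point beside the retention hypothesis, and a session denominator. It does not remove the mismatch, because Item 2 sets out to demonstrate safety and tolerability.

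A reader might go further and note that the threshold is met 41% of the time when true retention is only 80%, and infer that 20 is too few. The arithmetic is right (P(X ≥ 17) = 0.411 at p = 0.80), but the inference fails. That figure comes from judging an observed rate at its own threshold. Under the same rule it is 0.437 with 40 participants, 0.460 with 100 and 0.487 with 1,000. It says nothing about 20 in particular. Keeping 17/20 as a progression criterion leaves it unchanged, which is acceptable only if the criterion is labelled descriptive and the interval is shown.

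**Conclusion.** The point holds as a mismatch between claim and analysis. Twenty participants give an estimate of retention whose exact 95% interval spans about 35 percentage points at 17/20 (96.8 − 62.1 = 34.7), and they cannot exclude an event rate of up to 16.8% when no events are seen. A bare count on the Item 4 primary outcome does not show this.

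Two stronger readings are not supported. One is that 20 participants can never support retention above 80%: full retention would, with a lower limit of 83.2%, though its chance is 12% at a true rate of 90% and 36% at 95%. The other is that the sponsor will report 17/20 or zero events as proof: the documents do not say so.

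The figures assume 20 in the denominator and a strict inequality. If 16/20 also counted as success, the threshold would be met more often (0.415 at a true rate of 75%). The true rates of 70% to 95% are illustrations, since the documents give none. The intervals do not depend on them.

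**What to change.** Keep the sample size at 20 and change the wording and reporting:

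1. State in Item 2 and Statistical Hypotheses that the study estimates feasibility and safety. Present the 80% thresholds as descriptive progression criteria, for example at least 17 of 20 enrolled retained, and not as properties to be demonstrated.
2. Report retention at T1 (the Item 4 time point for attrition) and at T2, each with an exact 95% CI and all enrolled participants in the denominator. Name each time point in words, because the Data Analysis Plan numbers the visits T1 to T3 and puts the last at 12 weeks after surgery, where Item 4 has 8 weeks. Those passages must be reconciled.
3. State the session denominator for compliance and report it with an interval. Calculate it per participant, since sessions within one person are not independent. One option is the proportion of enrolled participants above 80%, with an exact CI.
4. Replace the hypothesis that the protocol will be safe with the proportion of participants having an intervention-related adverse event and the proportion having a serious adverse event, each with an exact 95% CI.

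This adds no participants, visits or measurements. It costs a less strong stated claim and a few extra calculations.
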